2.0 Abbreviations

ADA	Adalimumab
AE	Adverse Event
AMG	Arzneimittelgesetz (German Drug Law)
AS	Ankylosing Spondylitis
ASAS	Assessment of Spondyloarthritis International Society
ASDAS	Ankylosing Spondylitis Disease Activity Score
AST	Active supervised training
axSpA	Axial spondyloarthritis
BASDAI	Bath AS Disease Activity Index
BASFI	Bath AS Functional Index
BASMI	Bath Ankylosing Spondylitis Metrology Index
CA	Competent Authorities
CRP	C-reactive protein
EC	Ethics Committee
eCRF	electronic case report form
EDC	electronic data capture
Eow	Every other week
ESR	Erythrocyte sedimentation rate
EULAR	European League Against Rheumatism
HI	Health Index
HLA-B27	Human Leukocyte Antigen-B27
NIS	Non-interventional study
nr-axSpA	Non-radiographic axial spondyloarthritis
NRS	Numerical Rating Scale
NSAID	Nonsteroidal Anti-inflammatory Drug
PAM-13	Patient Activation Measure 13
PGA	Physician's Global Assessment
PMOS	Post Marketing Observational Study
PRO	Patient reported outcome
PTGA	Patient's Global Assessment
SAE	Serious Adverse Event
QoL	Quality of life
SAP	Statistical Analysis Plan
SOC	Standard of Care
VAS	Visual analogue scale
WAI	Work Ability Index

4.0 Abstract

Title: Treat and Train - A Post-Marketing-Observational Study (PMOS) to determine the effectiveness of combined adalimumab treatment and active supervised training in patients with axial spondyloarthritis

Rationale and Background: Although treated with effective medication many axSpA patients still do suffer from remarkable functional impairment and reduction in quality of life. Physical training is of fundamental importance for increasing and sustaining mobility, strength and physical fitness in general. This is also reflected in national and international guidelines, which strongly recommend physical training as the cornerstone of non-pharmacological treatment. However, there is a lack of recommendations concerning a definite type and intensity of appropriate exercise. Moreover, advice and prescription of physical training does not follow standardized procedures in Germany. In order to better understand the rational of physical training and thereby how to improve quality of health care for patients with axSpA, with this study we will analyze the impact of active supervised and standardized training in patients with axSpA.

Research Question and Objectives: This study is a non-interventional, longitudinal and non- confirmatory study to compare an active supervised training (AST) with standard of care (SOC) physiotherapy in patients with axial spondyloarthritis and stable response to Humira® (adalimumab) with respect to health-related outcomes. The primary objective is the improvement in spinal mobility after a 6 month training program. The active supervised training will be supplied by FPZ (Forschungs- und Präventions-Zentrum). SOC physiotherapy will be prescribed on physicians and performed on physiotherapist's discretion. Further objectives are the improvement in physical function, health-related quality of life, disease activity, pain, psychosocial risk factors and workability.

Study Design: Post-marketing observational study, multi-center, prospective, two-arm (Humira® + active supervised and standardized training vs. Humira® + standard of care physiotherapy), study duration 12 months from Baseline Visit.

Population: The selected study population will be adult patients (≥ 18 years of age) with a diagnosis of axSpA (ASAS Criteria 2009¹⁶) who meet the requirements per local label for treatment with Humira® (adalimumab). No prior treatment with biologic DMARDs is allowed. Patients must have initiated treatment with Humira® (adalimumab) based on current clinical practice criteria independent of the decision to participate in the study. Initiation of Humira®-treatment corresponds to the Enrollment Visit. Patients responding to Humira®-treatment based on physicians decision after 12 +/- 4 weeks and who are eligible for an active physiotherapy according to the rheumatologists and the physiotherapists estimation will be randomized to receive either an active supervised training or standard of care physiotherapy. Randomization of patients will be at Baseline Visit.

Variables:

Health-related outcomes will be assessed at the Enrollment Visit (initiation of Humira®-treatment), at Baseline Visit (after Randomization), after 3, 6, 9 and 12 month follow-up from baseline. For each follow-up time point a timeframe of \pm 4 weeks will be acceptable.

Primary outcome parameter:

- Spinal mobility as measured by the Bath Ankylosing Spondylitis Metrology Index [BASMI]; 6 month after Baseline Visit, a timeframe of \pm 4 weeks will be acceptable.

Secondary outcome parameters:

Time points of outcome parameter inquiry are listed in Table 1, chapter 9.1.

Improvement of spinal mobility

- Bath Ankylosing Spondylitis Metrology Index [BASMI]

Improvement of physical function

- Bath AS Functional Index [BASFI] NRS score (0 to 10)

Improvement of quality of life

- Overall functioning by ASAS Health Index (HI)

Reducing disease activity

- Disease activity as measured by Bath AS Disease Activity Index (BASDAI)
- Percentage of subjects achieving 50% improvement in BASDAI (BASDAI 50 response)
- Change from Baseline in disease activity measured by Ankylosing Spondylitis Disease Activity Score (ASDAS)
- Percentage of subjects achieving ASDAS major improvement
- Percentage of subjects achieving ASDAS clinically important improvement
- Percentage of subjects in ASDAS inactive disease (ASDAS < 1.3)
- Percentage of subjects with low disease activity (ASDAS < 2.1)
- Percentage of subjects with moderate disease activity (ASDAS ≥ 1.3 to < 2.1)
- Percentage of subjects with high disease activity (ASDAS ≥ 2.1 to < 3.5)
- Percentage of subjects with very high disease activity (ASDAS ≥ 3.5)
- Percentage of subjects achieving ASAS 20
- Percentage of subjects achieving ASAS 40
- Percentage of subjects achieving ASAS Partial Remission
- Change from baseline in Physician's Global Assessment of Disease Activity
- Change from baseline in Patient's Global Assessment of Disease Activity

Improvement of pain

- Change from baseline in Patient's Global Assessment of Pain
- Change from baseline in Patient's Assessment of Total Back Pain

- Change from baseline in Patient's Assessment of Nocturnal Back Pain

Improvement of other patient-reported outcomes

- Fatigue (BASDAI question 1)
- Duration and severity of morning stiffness (mean of BASDAI questions 5 and 6)

Psychosocial risk factors

- Fear avoidance behavior (FABQ)

Other variables to be analyzed include:

- Comorbid conditions
- Concomitant medications:
 - Prior and concomitant non-biologic disease-modifying antirheumatic drugs (DMARDs)
 - Concomitant systemic glucocorticoids
 - Concomitant pain relief medications: analgesics, non-selective non-steroidal anti-rheumatic drugs (NSAIDs), cyclooxygenase-2 (COX-2) inhibitors

Data Sources: Real-life observational data from clinical routine assessments in patient.

Study Size: 510 axSpA patients recruited from approximately 50 rheumatologist centers

Data Analysis:

Analysis populations:

Safety set: all patients enrolled and received at least one treatment with Humira®

ITT set: all patients randomized

Per protocol set (PPS): all patients randomized and performed AST or SOC physiotherapy until 6 months without severe protocol violations

Note: Several per protocol sets might be defined according coherence with AST and SOC treatment, respectively. Those specific PPS will be defined in SAP.

Background and demographic characteristics:

Continuously scaled variables will be described by mean, standard deviation, median, min, max, Q1 and Q3. Categorical variables will be described by counts and percentages.

Analysis of primary endpoint:

The primary analysis will be performed at ITT set.

The BASMI at 6 months (V5) will be analyzed within an ANCOVA with treatment as fixed effect and baseline BASMI (V3) as covariate. The treatment effect will be reported with its 95%-confidence interval. In case prerequisites of ANCOVA are not given, according methods might be applied (transformation of data).

Note: The BASMI (BASMI_{lin}) is continuously scaled, because it is the mean of 5 analog measures on a scale 0 - 10.

Analysis of secondary endpoints:

Continuously scaled variables with available baseline data will be analyzed like the primary endpoint. If baseline data are not available, 2-paired t-test will be applied.

The analysis of categorically scaled outcome variables by treatment will be performed by contingency tables. Related tests (χ^2 -Test, Armitage trend test) will be performed. Binary variables will be analyzed by logistic regression.

All treatment related effects will be reported with their 95% confidence interval.

Missing data and sensitivity analyses

(1)

Missing data within questionnaires (single items are missing) will be imputed questionnaire specific rules. If such rules does not exist, missing single items will be replaced by the mean or median (details: see SAP) of the other items of the respective patient at the specific visit, if no more than 25% of the items are missing. If more than 25% of items are missing, the whole score is set to missing.

(2)

One might expect that patients finish either the AST or the SOC physiotherapy for several reasons.

In case of less than 10% of missing data for primary outcome variable, the complete case analysis is efficient. In case of more missing data, the following approaches will be applied in the sense of sensitivity analyses.

First, the underlying mechanism will be investigated by logistic regression modelling (missing information y/n = f(baseline data, success of treatment between enrollment and baseline assessment)). In case of MCAR (missing completely at random) the analysis will be performed at complete cases. In case of MAR (missing at random), multiple imputation might be applied in a sensitivity analysis. In case of MNAR (missing not at random) a specific analysis is not possible, and scenario assuming several drop-out scenario will be investigated. Such sensitivity analyses (e. g. last observation carried forward, baseline value is carried forward, missing AST will be imputed by respective SOC data) will be defined in statistical analysis plan.

Assessment of covariates

Within primary model further influencing variables (baseline data, data describing success of treatment between enrollment and baseline assessment) might be investigated. Details will be provided in SAP.

Centers could be regarded as random effects within these models (mixed models) to investigate homogeneity of the effects.

Safety data

Safety data will be described using the safety set. The data will be presented by intensity, requirement of treatment, system organ class, causality, outcome, action taken

Sample size

Assuming a treatment effect of 1 point, a standard deviation of 3.7 points and choosing 5% and 20% for type I as well as type II error, respectively, 216 patients per group are necessary. Taking into account 15% drop-out, a final study size of **510** results (216 * 2 * 1/0.85).

Data review and SAP

Data will be investigated in a blinded data review meeting in terms of protocol violations and missing data. Consequences for analysis will be taken into account in the SAP.

Complete and specific details of the final statistical analysis will be described and fully documented in the Statistical Analysis Plan (SAP). The SAP will be finalized prior to the database lock.

A final study report will be written. This report will contain a description of the objectives of the study, the methodology of the study and its results and conclusions.

Milestones:

Start of Data Collection Q1 2017

End of Data Collection Q3 2019

Final Report of Study Results Q2 2020

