Patient's Global Assessment of Disease Activity	X	X	X
modified WAI	X	X	X
Patient's Global Assessment of Pain NRS	X	X	X
Patient's Assessment of Total Back Pain NRS	X	X	X
Patient's Assessment of Nocturnal Back Pain NRS	X	X	X
Fear avoidance behavior questionnaire (FABq)	X	X	X

9.2 **Setting**

Approximately 510 patients with axSpA (ASAS Criteria 2009¹⁶) who receive humira® (adalimumab) according to the local product label and who fulfill the study eligibility criteria will be enrolled. It is expected that the number of 510 patients treated with humira® is sufficient to meet the objectives of this PMOS. Approximately 50 rheumatologists will contribute to enroll eligible patients in this study.

Patients who consent to participate in the study will be observed for up to 12 month from baseline. Physicians should treat enrolled axSpA patients just as they treat axSpA patients in the routine clinical practice. Patients may discontinue humira® treatment or the study at any time for any reason. Following discontinuation of humira®, the patient will be treated in accordance with the investigator's best clinical judgment.

If the reason for treatment discontinuation is due to an adverse event, the event must be reported as follows:

- SAE: reported to AbbVie within 24 hours of physician awareness
- Non serious AE: reported to AbbVie within 24 hours of physician awareness

Patients that end humira® treatment or start treatment on any other biologic marketed in the EU will be withdrawn from the study and will not be part of the primary analysis population.

If a patient withdraws or is lost to follow-up, every effort should be made to note such along with the reason for withdrawal in the electronic case report form (eCRF).

Inclusion Criteria

A patient will be eligible for study participation if he/she meets the following criteria:

- Patients diagnosed with axSpA (either AS or nr-axSpA), fulfilling the ASAS classification, aged at least 18 years
- Prescription of humira® for treating axSpA according to the local product label

- Eligibility for active physiotherapy according to the rheumatologist and physiotherapist
- Patients must have signed written informed consent before starting any study-related assessments or procedures

Exclusion Criteria

A patient will not be eligible for study participation if he/she meets any of the following criteria:

- Patients with total spinal ankylosis based on the investigators' assessments of available radiographs

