##### 4.4.2 Secondary study endpoints

The following secondary study endpoints, which concern changes from baseline, are assessed at all visits (after 3, 6, 8 and 12 months).

- (2) Improvement in spinal mobility – BASMI
- (3) Improvement in physical functioning – BASFI NRS score (0 to 10)
- (4) Improvement in quality of life – general functioning assessed by ASAS-HI
- (5) Reduction in disease activity
  - Disease activity assessed by BASDAI
  - Percentage of study participants achieving a 50% improvement in BASDAI score (BASDAI50 response)
  - Change in disease activity from baseline assessed by ASDAS (Ankylosing Spondylitis Disease Activity Score)
  - Percentage of study participants achieving ASAS major improvement
  - Percentage of study participants achieving ASDAS clinically important improvement

- f. Percentage of study participants in ASDAS inactive disease (ASDAS < 1.3)
- g. Percentage of study participants with low disease activity (ASDAS < 2.1)
- h. Percentage of study participants with moderate disease activity (ASDAS ≥ 1.3 to < 2.1)
- i. Percentage of study participants with high disease activity (ASDAS ≥ 2.1 to < 3.5)
- j. Percentage of study participants with very high disease activity (ASDAS ≥ 3.5)
- k. Percentage of study participants achieving ASAS20
- l. Percentage of study participants achieving ASAS40
- m. Percentage of study participants achieving partial ASAS remission
- n. Change from baseline in physician's global assessment of disease activity
- o. Change from baseline in patient's global assessment of disease activity

(6) Reduction in pain

- a. Change from baseline in patient's global assessment of pain
- b. Change from baseline in patient's assessment of total back pain
- c. Change from baseline in patient's assessment of nocturnal back pain

(7) Improvement in other PROs

- a. Fatigue (BASDAI Question 1)
- b. Duration and severity of morning stiffness (mean of BASDAI Questions 5 and 6)

(8) Psychosocial risk factors – FABQ

(9) Other variables proposed for assessment:

- a. Comorbidities (screening only)
- b. Comedication:
  - i. previous and concomitant non-biologic DMARDs
  - ii. concomitant systemic glucocorticoids
  - iii. concomitant pain medication: analgesics, NSAIDs, cyclooxygenase-2 (COX-2) inhibitors

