#### (2) Secondary outcome measures/endpoints

Continuous variables for which baseline data are available will be assessed in the same way as the primary outcome variable. Assessments take place at all follow-up visits (after 3, 6, 9 and 12 months).

In the absence of baseline data, the robust t-test for independent samples will be used.

Discrete outcome variables depending on treatment are assessed using contingency tables. Simple analyses for the presence of an association will be performed using a chi square test (possible Fisher's exact test in the presence of small sample sizes), and studies for associations with ordinal variables will be done using the Cochrane-Armitage test for trend.

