#### (2)

There are various reasons for assuming why patients complete the AST or SOC physiotherapy.

If less than 10% of values are missing for the primary outcome variable, complete case analysis is effective. If more values are missing, various approaches meeting the criteria of sensitivity analyses are employed that cover a worst-case and a best-case scenario.

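### No method is stated for missed visits in the continuous secondary endpoints, so the separate ANCOVAs at months 9 and 12 rest on patients still observed and ignore earlier follow-up scores

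*Protocol*

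**What the plan says.** **Model.** Protocol 4.0 and 9.7.4: "Continuously scaled variables with available baseline data will be analyzed like the primary endpoint". The model being copied is a single-visit one: "The BASMI at 6 months (V5) will be analyzed within an ANCOVA with treatment as fixed effect and baseline BASMI (V3) as covariate". SAP 6.3(2) agrees ("Continuous variables for which baseline data are available will be assessed in the same way as the primary outcome variable") and adds the visits: "Assessments take place at all follow-up visits (after 3, 6, 9 and 12 months". SAP 4.4.2 differs on the third visit, since its secondary endpoints "are assessed at all visits (after 3, 6, 8 and 12 months"; the schedule in SAP 5.1 has month 9. The only mixed model planned (SAP 6.5) has site as a random effect and is for the primary outcome alone.

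**Missing items.** Protocol 9.7.5(1) and SAP 6.4(1) apply questionnaire-specific rules, or else replace an item from the patient's other items at that visit. Protocol: "If more than 25% of items are missing, the whole score is set to missing".

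**Missed visits.** SAP 6.4(2): "If less than 10% of values are missing for the primary outcome variable, complete case analysis is effective". With more missing, it announces sensitivity analyses covering a worst and a best case, which it does not define. Protocol 9.7.5(2) has the same trigger and a fuller list: a model for missingness, possible multiple imputation, carry-forward, and SOC data in place of missing AST data. Neither text names a secondary endpoint or a visit other than the primary one.

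**Withdrawal.** Under Protocol 9.2, patients who end adalimumab or start another biologic "will be withdrawn from the study and will not be part of the primary analysis population"; SAP 4.5 says the same. The ITT set (Protocol 9.7.1, SAP 6.1) is all randomised patients.

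**The concern.** A single-visit ANCOVA uses only patients with a value at that visit. A patient seen at months 3 and 6 who then leaves contributes nothing to the month-12 comparison, although those two scores help to predict the missing one. The estimate is unbiased only if, given the V3 value and treatment, leaving is unrelated to how the patient fared after V3, or if any such relation affects both arms alike.

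The design gives reason for doubt. Ending or switching the drug means leaving the study, and such a step may well follow poor disease control, which BASDAI, ASDAS and the pain ratings measure. Protocol 9.5 also lists the physical exposure of patients among its reasons for expecting dropout, and the arms may differ in that respect. The 9- and 12-month results are the most exposed, because losses accumulate. They are also the ones that show whether any benefit outlasts the 20-week training course.

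**Working it through.** **1. The plan's own figure.** The documents give no figure for the secondary analyses, only the sample size for the primary. Inputs: difference 1, SD 3.7, two-sided 5% (sidedness is not stated, but one-sided gives 170), power 80%.
- Normal formula: 2 × (1.960 + 0.842)² × 3.7² / 1² ≈ 215 per arm. The t-test version gives 215.9, so 216, as stated.
- Dropout: 216/0.85 = 254.1, so 255 per arm and 510 in total, as stated.

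**2. Number of comparisons.** BASMI, BASFI, ASAS-HI, BASDAI, ASDAS, physician's global, patient's global, three pain ratings, fatigue, morning stiffness and FABQ make 13. Modified WAI makes 14. Counting the two FABQ scores separately makes 15. Over four visits: 13 × 4 = 52 to 15 × 4 = 60 separate ANCOVAs, including BASMI at month 6, which is the primary.

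**3. Patients left out.** Assume the planned 15% loss applies to 510 randomised patients and is spread evenly over V4–V7, that is 3.75% before each visit.
- With a month-12 value: 0.85 × 510 ≈ 433.
- With at least one follow-up value: 0.9625 × 510 ≈ 491.
- About 57 patients (11.25% of 510) have follow-up scores that the month-12 ANCOVA ignores.

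**4. Bias.** With e the month-12 residual given treatment and V3, the bias is E[e | observed, AST] − E[e | observed, SOC]. It vanishes when selection is the same in both arms. Simulation with residual SD 1, equal correlation r between visits, true difference 0 and about 14% lost by month 12, where dropout in one arm only depends on the last observed score:

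| r | log-odds per SD | per-visit ANCOVA | repeated-measures |
|---|---|---|---|
| 0.5 | 0.7 | −0.054 | −0.004 |
| 0.5 | 1.5 | −0.088 | 0.005 |
| 0.7 | 0.7 | −0.072 | 0.000 |
| 0.7 | 1.5 | −0.127 | 0.000 |
| 0.9 | 0.7 | −0.092 | −0.003 |
| 0.9 | 1.5 | −0.161 | −0.002 |

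With the same mechanism in both arms, both methods stayed within 0.006 SD of zero. Exchanging the arms reverses the sign.

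On a scale with SD 2.0, 255 per arm, true month-12 difference −0.40 and 11–22% loss, the per-visit ANCOVA gave about −0.29 to −0.48 when outcome-related dropout differed by arm. The repeated-measures estimate stayed within about 0.01 of −0.40. The range is illustrative, not a bound. In further runs with correlation 0.75^√lag:
- Log-odds slopes of 0.2 (SOC) and 1.0 (AST) gave −0.47 at 12%/14% loss and −0.50 at 19%/21%.
- Slopes of 1.0 (SOC) and 0.5 (AST) gave −0.38 and −0.36.
- Equal slopes gave −0.40 to −0.42.

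**5. Scale of the shift.** With that correlation, V3 to V7 is 0.75² = 0.5625 and the residual SD is 2.0 × √(1 − 0.5625²) = 1.65. With 13% lost, 222 per arm remain and the SE is 1.65 × √(2/222) ≈ 0.16. A shift of 0.06 is then about 0.4 SE, and one of 0.11 about 0.7 SE.

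**6. Precision.** The variance from the joint model is the month-12 element of the inverse of Σ n·w_k·C_k⁻¹ over dropout patterns k, against 1/[n(1 − d)] for the ANCOVA (unit residual variance). At d = 15%, with residual correlation 0.3–0.9 (compound symmetry or AR(1)), the ratio is 0.901 to 0.996. Since √0.901 = 0.949 and √0.996 = 0.998, the SE is 0.2% to 5% smaller, with 5% only at correlation 0.9. The SD 2.0 simulations showed about 0–3%.

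**The case against.** Several stronger readings are tempting, and the documents do not support them.

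- *A reader might infer that the secondaries have no missing-data method at all.* That is wrong. The item-level rules cover BASFI, BASDAI, ASAS-HI and the other multi-item scores. The visit-level rules may also carry over, because the secondaries follow the primary and SAP 6.3 says the sensitivity analyses serve the primary in particular, which is not the same as only. What stands is an unstated scope. Even if the rules extend, they add sensitivity analyses, and the main per-visit estimate still uses completers.
- *A reader might infer that the plan overstates the benefit of training, perhaps by about 20%.* That takes dropout that depends more steeply on outcome in AST and about 20% loss. The documents give one overall 15%, with no split by arm, visit or outcome. With the steeper slope in SOC, the benefit is understated.
- *A reader might infer that a joint model uses all the data.* It uses all observed follow-up values. A patient with no V4–V7 value adds nothing.

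It is also fair to say that baseline-adjusted ANCOVA by visit is a valid method, that the study is described as non-confirmatory and exploratory, and that the SAP deliberately makes no multiplicity correction. This lowers the priority. It does not remove the point, because the plan promises a 95% interval for every treatment effect, and an interval centred on a biased estimate misleads in an exploratory study too.

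Finally, if patients who stop adalimumab are excluded from the analysis altogether, a joint model recovers nothing from them. That objection stands, and the fix has to deal with it.

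**Conclusion.** The point holds as a gap in the plan with a better method available. About 13–15 continuous secondaries are compared visit by visit, and no method for missed visits or dropout is stated for them. Late comparisons default to patients still observed.

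The consequence is conditional. If outcome-related dropout differs by arm, bias of about 0.05–0.16 residual SD is plausible near the planned loss, in a direction that cannot be known beforehand. If dropout works alike in both arms, little is lost. Dropout by arm and visit, the SD of 2.0 and the correlations are assumptions, since the documents give none of them for these endpoints. The change is advisable rather than essential: it bears on exploratory secondary results, and the primary test and the 510 patients are untouched.

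**What to change.** 1. In SAP 6.3(2) and Protocol 9.7.4, analyse each continuous secondary by one mixed model for repeated measures over V4–V7. Fixed effects: treatment, visit, treatment-by-visit, V3 value and V3-by-visit. Use an unstructured within-patient covariance. Include all observed follow-up values of randomised patients, and report the AST–SOC difference with its 95% CI at each visit.
2. Keep the per-visit ANCOVA as a supplementary table.
3. State that values recorded before a patient is withdrawn for stopping adalimumab are kept in this analysis. Reconcile Protocol 9.2 and SAP 4.5, which remove such patients from the primary analysis population, with the ITT set of all randomised patients.
4. State whether Protocol 9.7.5(2) and SAP 6.4(2) apply to secondary endpoints.
5. Reconcile month 8 in SAP 4.4.2 with month 9 in SAP 6.3(2) and the visit schedule.

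**Cost.** Wording and programming in the SAS 9.4 already named, with no extra patients or visits. The model assumes missing at random given the observed scores, so it does not cover loss driven by unobserved scores. Its estimate refers to outcomes as if patients had stayed on study, and the SAP should say so.
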